### **Analytical Plan**

**Primary outcome:** The IKDC Subjective Knee Evaluation Form score will be the primary outcome measure. The IKDC subjective knee form contains 19 questions and requires approximately five minutes to complete.(2) All except one of the items is converted to a score; a

maximum score of 100 indicates that the patient has no restrictions in their daily activities or sports and does not have any knee symptoms.(2)

**Secondary outcome:** Pain levels and the use of pain medication will be monitored by study participants using a daily pain diary. The pain diary will be used for the first two weeks after surgery. Pain levels will also be collected at the 1 and 4 day telephone calls. A pain rating will also be collected at the one week, 30 day, three months, six months, and one year visit.

**Data management:** All study data will be entered into a REDCap database. The database will be HIPAA compliant and will meet all the requirements of the NIH and FDA. The REDCap server is behind a firewall and is backed up every 24 hours. The data will be sent as an Excel spreadsheet for analysis to biostatisticians in the Section on Biostatistics of the Department of Public Health Sciences at Wake Forest School of Medicine.

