### **Objectives**

This randomized, controlled clinical trial will compare the outcomes of single portal versus two portal techniques in patients who have meniscus or articular cartilage pathology. The study hypothesis is that patients who undergo single portal arthroscopy will have less pain post-operatively, use less pain medication, and have a higher International Knee Documentation Committee (IKDC) score at six months and one year compared to patients who undergo traditional two portal knee arthroscopy.

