### **Sample Size:**

Power calculations were performed based on data from previous studies. Van de Graaf found a standard error of the mean (SEM) of 5.3 and a smallest detectable difference (SDD) of 14.6 for the Subjective Knee Evaluation Form part of the International Knee Documentation Committee (IKDC).(2) These measures were slightly larger than the SEM of 4.6 and the SDD of 9.0 reported by Irrgang.(1) Based on these values, power calculations identified the desired sample size as 50 patients in each surgical group to yield 84.7% power to detect a difference with an alpha = 0.05. In order to account for 10% missing data due to patient drop-outs and/or loss to follow-up, a total of 110 patients will be randomized and enrolled with 55 patients in each of the two surgical groups. The blocked randomization scheme will be designed for the potential enrollment of 60 patients in each of the two study groups.

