## Interventions and Interactions

### Evaluation Schedule Summary:

Evaluation	History / Pre-Op	Intra-Op	1 day	4 days	1 week	30 days ± 7 days	3 months ± 2 weeks	6 months ± 2 weeks	1 year ± 1 month
Patient • IKDC demographics	X								
• IKDC current health	X							X	X
• IKDC subjective knee evaluation	X					X	X	X	X
Patient phone calls • Pain scores/pain medication log			X	X					
Physician • IKDC knee history	X								
• IKDC surgical documentation form		X							
• IKDC knee examination form	X					X	X	X	X
• Document rehab duration						X	X		
Stitch Removal/ Postop Follow-up for Pain/Meds					X				

The study will include six visits: one pre-surgery visit and five post-surgery visits at one week, 30 days, three months, six months, and one year. The one week, 30 day, and three month follow-up visits coincide with the standard of care follow-up visits for patients who undergo knee arthroscopy. The six month and one year visits will be for research purposes and will not be billed to insurance providers.

Additionally, the patients will be contacted by phone at 1 and 4 days after surgery to determine their visual analog pain scores and their use of pain medications. Patients will also keep a daily log of their pain level and use of pain medications. These calls will also be used to remind patients to complete their pain diaries.

*Randomization:* A blocked randomization scheme (block size of 10) will be used to assign study participants to either single portal (Group 1) or two portals (Group 2) knee arthroscopy. Prior to surgery, the surgeon will log on to the randomization website to determine each participant's surgical group assignment. After randomization for each patient is complete, the website will document the name of the person who logged on to perform the randomization, the date and time of the log in, and the surgical group assignment for each patient. In addition, the website will document the patient's name, medical record number, and study treatment allocation. This randomization information will be forwarded to the operating room staff so that they can prepare for each study participant's surgical procedure.

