## **Outcome Measures**

### **Patient assessments:**

Patients will complete the patient-related IKDC questionnaires at each study visit except the one week visit. The IKDC is used to monitor knee symptoms, function, and activity level (1) The IKDC was developed and revised by knee experts as a knee-specific rather than a disease-specific evaluation. (1) A recent study by Van de Graff, et al demonstrated that the IKDC was better in all its measurement properties than the KOOS or the WOMAC for evaluating patients with meniscal injuries. (2)

At the pre-surgery visit, study participants will complete several components of the IKDC questionnaires including the demographic form, current health assessment form, and the subjective knee evaluation form. Patients will maintain a daily log to document their use of pain medications for the first two weeks after surgery. In addition, study participants will complete the subjective knee evaluation form at one month, three months, six months, and one year.

Patients will be contacted by phone on post-surgical days 1 and 4 to remind them to complete their daily log and to report their pain level and medication use. At each phone call and clinic visit, patients will be asked two questions: *1. What day did you feel that you had completed recovering from the surgery?* and *2. What day did you stop taking pain medicine?* Patients also will be asked these questions at the 30 day clinic visit.

If patients are unable or decline to return to clinic for follow-up, we will try to collect the patient-completed questionnaires either by telephone, by mail, or by a web-based link sent to them via a REDCap database survey at any study time point.

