### **Physician assessments:**

The principal investigator will complete the IKDC knee history form, surgical documentation form and knee examination form at baseline. At 30 days, three months, six months, and one year the physician assistant or other designee will complete the knee examination form. Additionally, the rehabilitation duration will be noted at the 30 days and three month visit per patient report.

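### The primary IKDC comparison has no fixed time point or test, and the scheduled pre-operative score has no role; naming one time point and adjusting for baseline costs only wording

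*Combined protocol and SAP*

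**What the plan says.** The Analytical Plan states: "The IKDC Subjective Knee Evaluation Form score will be the primary outcome measure". It then describes the form and its scoring, and says that biostatisticians will receive the data. It gives no time point, test, model or covariate, and does not say whether the follow-up score or the change from before surgery is compared.

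Two other sections bear on the gap without closing it:

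- **Objectives.** The hypothesis is that single-portal patients will "have a higher International Knee Documentation Committee (IKDC) score at six months and one year". Neither time point is ranked, and the rule for success across the two is not stated.
- **Sample Size.** The target is "50 patients in each surgical group to yield 84.7% power to detect a difference with an alpha = 0.05". The difference, the between-patient SD, the time point, the test and its sidedness are not given.

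The pre-operative score is in the schedule. The Evaluation Schedule Summary marks the row "IKDC subjective knee evaluation" before surgery and at 30 days, three months, six months and one year. Patient assessments lists the pre-surgery forms, "including the demographic form, current health assessment form, and the subjective knee evaluation form", and adds that "study participants will complete the subjective knee evaluation form at one month, three months, six months, and one year". The screening and enrollment text also has the form completed after consent. No section gives the pre-operative score a use in the analysis.

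**The concern.** Two things are at stake.

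The first is the error rate. With two candidate time points and no rule joining them, the primary result can be settled after the data are seen. Whether that inflates type I error depends on how the two time points combine, which is what the plan leaves unsaid.

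The second is precision. A pre-operative measurement on the same instrument usually predicts part of the follow-up score, and adjusting for it narrows the interval in proportion to that prediction. The plan schedules the measurement and then leaves it unused. It also leaves room for a change-score analysis, which loses power against the plain follow-up comparison whenever the pre- to post-operative correlation is below 0.5 (with equal SDs).

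This is a matter of precision and prespecification, not bias. In a randomized comparison, chance baseline imbalance is already covered by the unadjusted standard error.

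**Working it through.** **Inputs.** From Sample Size: 50 per group, 84.7% power, alpha 0.05. Enrolment of 55 per group already allows for 10% loss (55 × 0.9 = 49.5), so 50 is the right number to analyse. Assumed here: two-sided test; pre- to post-operative correlation r from 0.1 to 0.6; between-visit correlation 0.5 or 0.7; equal SDs before and after surgery for the change score.

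**1. The plan's own figure.** The 84.7% cannot be rebuilt. Using the quoted SEM as an SD and the SDD as the difference (14.6/5.3 or 9.0/4.6) gives power near 100%. Working backwards with a two-sided t-test, 50 per group and 84.7% power imply a standardized difference d = 0.603. That corresponds to an SD of 9.0/0.603 ≈ 14.9 or 14.6/0.603 ≈ 24.2, neither of which is stated. The d is therefore only a common yardstick. The noncentrality of the unadjusted test is d × √(50/2) = 0.6027 × 5 = 3.013.

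**2. Power by analysis, 50 per group.**

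- Adjusted: noncentrality 3.013 / √[(1 − r²)(1 + 1/(2n − 4))], df 97. The second factor, 1 + 1/96 = 1.0104, is the cost of estimating the slope. At r = 0.3: 3.013 / √(0.91 × 1.0104) = 3.142, power 87.5%.
- Change score: noncentrality 3.013 / √(2 − 2r), df 98. At r = 0.3: 3.013 / √1.4 = 2.547, power 71.3%.

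| r (assumed) | Follow-up alone | Baseline-adjusted | Change score | CI width, adjusted ÷ unadjusted |
|---|---|---|---|---|
| 0.1 | 84.7% | 84.7% | 60.4% | 1.000 |
| 0.2 | 84.7% | 85.7% | 65.5% | 0.985 |
| 0.3 | 84.7% | 87.5% | 71.3% | 0.959 |
| 0.5 | 84.7% | 92.9% | 84.7% | 0.871 |
| 0.6 | 84.7% | 96.0% | 91.6% | 0.804 |

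**3. Type I error under each reading of the two time points.**

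- *Either counts, one fixed analysis.* Independent tests would give 1 − 0.95² = 9.75%. Tests correlated 0.5 give 9.1%, and correlated 0.7 give 8.3%. Baseline adjustment lowers the correlation slightly (at r = 0.3, (0.5 − 0.09)/0.91 = 0.45), so the adjusted test stays at about 9%.
- *Both required, one fixed analysis.* The rate cannot exceed the 5% of a single test.
- *Either counts, and the follow-up, change and adjusted analyses all stay open.* Simulation at r = 0.3 and between-visit correlation 0.5 gives 16.1% when a result in either direction counts. Counting only results that favour single portal, it is 8.2%.
- *Both required under the same analysis, that analysis freely chosen.* The same simulation settings give 2.3%.

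**The case against.** The strongest reply is that the hypothesis joins its time points with *and*. Read as requiring both, the plan does not inflate type I error at all. That reading is natural and the documents allow it. They do not state it, though, and the Sample Size section does not power for it, so the rule still has to be written down.

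A reader might infer from the open choices that the trial runs at 16% type I error. The documents do not support that. The figure needs three competing analyses, success at either time point and results counted in both directions, whereas the hypothesis is directional and speaks of a higher score at follow-up. No section proposes a change score. The 71% power at r = 0.3 therefore warns against one possible choice; it does not describe the plan.

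It is also fair to say that an unadjusted randomized comparison is valid, so adjustment is a preference for precision. Against the follow-up comparison that the hypothesis suggests, the gain is 0, 1.0 and 2.8 points at r = 0.1, 0.2 and 0.3. Larger gains need correlations that the documents do not supply. This stands, and it is why the gain is given as a range.

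Two further inferences should be resisted. The pre-operative score is scheduled; the documents do not show that it was completed. Nor would adjustment rescue a trial cut short by the sponsor's withdrawal of support: if 30 per group remained (an assumption, since the Update section gives no count), power at r = 0.3 would be 66.4% adjusted against 63.1% unadjusted.

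**Conclusion.** The point holds at moderate size. The firm part is the missing specification: no section fixes the time point or the comparison for the primary outcome, or says whether success at six months, one year or both is required. If either suffices, two-sided type I error is about 9% even with a single adjusted analysis; if both are required, it is not inflated.

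The second part is a precision gain available without new data collection, from essentially nothing at r = 0.1, through about 3 points at r = 0.3, to about 11 points at r = 0.6 (96.0 − 84.7 = 11.3). These levels rest on a 84.7% that cannot be rebuilt, a two-sided test and assumed correlations. The ordering of adjusted against unadjusted depends on none of the plan's missing inputs, apart from a trivial slope cost when r is near 0.1.

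**What to change.** Add to the Analytical Plan:

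> The primary comparison is the single- minus two-portal difference in IKDC subjective score at [six months or one year: name one], by randomized group, from a linear regression on treatment group and pre-operative IKDC subjective score, with a two-sided 0.05 test and 95% confidence interval. The other time point is secondary and analysed the same way.

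This should be dated before data are seen by arm. If they have already been seen, the choice should be labelled post hoc in the report. The Objectives should be aligned with the time point chosen.

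The cost is a few lines of wording, with no new visits, forms or patients. The downside is essentially no gain if the pre-operative score predicts outcome weakly. The words *by randomized group* settle the analysis group for this comparison: the protocol keeps cross-over patients in the study but does not say in which group they are analysed. Which forms are collected at the close-out visit is a separate question and is not part of this point.

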### **Subject Recruitment Methods**

The study will recruit patients who present to the Orthopaedic Sports Medicine Clinic at Wake Forest Baptist Health with symptoms requiring arthroscopic knee surgery for meniscal or articular cartilage pathology.

**Study screening and enrollment:** Potential study participants will be screened in the Orthopaedic Sports Medicine Clinic. Patients with meniscus injuries who meet the study inclusion criteria will be told about the study and will be asked if they would like to participate. The study will be described, and the requirements for study participation will be explained. Potential study participants will be encouraged to ask questions about the study and to find out what is involved in study participation. A patient information sheet will be provided to the potential subject to explain the study and used as a recruitment tool. Patients who agree to

participate will be asked to provide informed consent. No study related procedures will occur until after the informed consent is obtained. Following completion of informed consent, the study participants will be asked to complete three of the six IKDC forms including questionnaires to document demographics, current health, and subjective knee evaluations.

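### Pain and pain-medication use are hypothesised effects but have no scheduled pre-operative measurement on the same scale, which costs precision, though not validity, in these secondary comparisons

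*Combined protocol and SAP*

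**What the plan says.** The Objectives section states the expectation that "patients who undergo single portal arthroscopy will have less pain post-operatively, use less pain medication", alongside a higher IKDC score at six months and one year. In the Analytical Plan the IKDC subjective score is primary, and pain and pain-medication use are secondary.

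Pain and medication are to be measured as follows:

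- **Telephone calls.** Under Evaluation Schedule Summary, patients are "contacted by phone at 1 and 4 days after surgery to determine their visual analog pain scores and their use of pain medications". The Analytical Plan repeats this: "Pain levels will also be collected at the 1 and 4 day telephone calls".
- **Diary.** "The pain diary will be used for the first two weeks after surgery".
- **Clinic.** "A pain rating will also be collected at the one week, 30 day, three months, six months, and one year visit". The schedule table also has a one-week row for pain and medication follow-up.

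In the schedule table, the row "Pain scores/pain medication log" is marked at day 1 and day 4 only, and its History/Pre-Op cell is empty. The pre-operative column contains only IKDC forms: demographics, current health, subjective knee evaluation, knee history and knee examination. Subject Recruitment Methods agrees, saying that after consent patients complete "three of the six IKDC forms including questionnaires to document demographics, current health, and subjective knee evaluations".

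The Analytical Plan names no statistical model and no covariate for any outcome.

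**The concern.** Pain and analgesic use after surgery are likely to depend partly on pain and use before it. The Exclusion Criteria remove long-standing analgesic users and patients with chronic pain from other causes. They do not remove pain from the knee to be operated on, or short-term analgesic use. Some variation at entry should therefore be expected, and the plan has no instrument to record it on the scale used afterwards.

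Three things are at stake. First, variation that a baseline covariate could explain stays in the error term. Second, a chance difference between arms in entry pain or analgesic use cannot be seen or adjusted for directly. Third, pain after surgery cannot be expressed as a change from before surgery on the same scale. There is also a smaller interpretive problem. Patients are asked on which day they stopped pain medicine. With no pre-operative record, a late date from someone who was already taking analgesics looks the same as a slow recovery.

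The primary outcome does not share the gap, because the IKDC subjective form is completed pre-operatively and at four follow-up visits.

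**Working it through.** **1. The plan's own figure.** The only power statement (Sample Size) is 84.7% with 50 per group at alpha 0.05, for the IKDC. It cannot be reproduced, because neither the target difference nor the between-patient SD is stated. Two-sided, it implies a standardised difference of (1.960 + 1.024) × √(2/50) = 0.597. It does not concern pain or analgesic use, so nothing below depends on it. No precision figure is given for the pain outcomes.

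**2. Timing of measurements, set side by side.**

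| Measure | Before surgery | After surgery |
|---|---|---|
| IKDC subjective form | yes | 30 days, 3 months, 6 months, 1 year |
| Visual analog pain score by phone | none shown | days 1 and 4 |
| Pain and medication diary | none shown | two weeks |
| Clinic pain rating | none shown | 1 week to 1 year |
| Medication use by phone | none shown | days 1 and 4 |

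**3. Precision available from a baseline.** Adjusting for a baseline with pre/post correlation r multiplies the residual variance by 1 − r². The same precision without adjustment needs N/(1 − r²) patients. N = 110 is the planned enrolment (Sample Size). The documents give no r, so 0.2 to 0.5 is assumed.

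| r | 1 − r² | Variance removed | 110/(1 − r²) |
|---|---|---|---|
| 0.2 | 0.96 | 4% | 114.6, about 115 |
| 0.3 | 0.91 | 9% | 120.9, about 121 |
| 0.5 | 0.75 | 25% | 146.7, about 147 |

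The standard error is multiplied by √0.96 = 0.980 at r = 0.2 and by √0.75 = 0.866 at r = 0.5, so confidence intervals narrow by about 2% to 13%.

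In terms of detectable effect, with 50 analysed per group, 80% power and two-sided alpha 0.05, the unadjusted value is (1.960 + 0.842) × √(2/50) = 0.560 SD. It becomes 0.549 SD at r = 0.2 and 0.485 SD at r = 0.5.

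**4. Chance imbalance.** With 55 per group, the difference in mean baseline pain has SD √(2/55) = 0.191 baseline SDs. An imbalance above 0.2 SD in either direction therefore has probability of about 0.29 (0.2/0.191 = 1.05). Its effect on the outcome difference is r × 0.2, which is 0.04 SD at r = 0.2 and 0.10 SD at r = 0.5. This variation is already in the unadjusted standard error. It is the same loss as in step 3 seen from another side and must not be counted twice.

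**5. What the IKDC already offers.** The pre-operative IKDC subjective score reflects knee symptoms and could be a covariate now. The further gain from a pain baseline is what it explains beyond that score. The documents give no correlation from which to compute this. Because the two measures overlap, the gain should be somewhat below the figures in step 3.

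**The case against.** A reader might infer that, without a baseline, the design cannot separate differences in entry pain from the effect of the second portal. The documents do not support that. Assignment is by blocked randomization to two equal groups, so entry pain is balanced in expectation. The hypothesis compares post-operative values between groups, and that comparison is valid without a baseline. Nor is the 29% chance of an imbalance above 0.2 SD an added harm, since the test's error rate already allows for it.

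Other objections carry weight:

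- **Priority.** The pain hypotheses come first in the sentence in Objectives, but word order is not rank. The Analytical Plan makes them secondary.
- **Existing proxy.** The IKDC forms carry some information on pain. The section on the study's closure describes a survey about function and pain and identifies it with IKDC forms, one of which, Current Health, is a pre-operative patient questionnaire. This reduces the gap for pain. No comparable proxy is described for analgesic use.
- **Low correlation early on.** Pain on days 1 to 4 follows fresh surgery and analgesia, so r may be lowest there and the gain small. The range therefore starts at 0.2.
- **Unseen forms.** The Appendix lists the questionnaires and pain logs but their content is not available, so the absence of a pre-operative pain or medication item is read from the schedule and the form titles. The clinic rating from 30 days on might be an IKDC item, which would have a baseline. Against this, the same sentence includes the one-week visit, when no IKDC patient form is completed. The text does not settle the matter.

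What stands is that no instrument described as measuring the pain and medication outcomes is scheduled before surgery, and the plan gives no reason.

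**Conclusion.** The point holds as a modest loss of efficiency in two secondary outcomes. It is not a source of bias and does not touch the primary outcome. Under an assumed pre/post correlation of 0.2 to 0.5, a like-for-like baseline would remove 4% to 25% of residual variance, equivalent to about 115 to 147 patients in place of 110. The lower end is more plausible for days 1 to 4, and the gain beyond baseline IKDC is somewhat smaller throughout. The ratio, 1.04 to 1.33, applies equally to whatever number is finally analysed.

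Change from baseline on the pain scale is also unavailable, unless the later clinic rating proves to be an item of a form completed pre-operatively. That does not mean the trial can show no improvement at all: the IKDC subjective score, which includes symptoms, can be compared with its own baseline.

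The Update to the study protocol reports that the sponsor has withdrawn support, and a pre-randomization value cannot be recovered afterwards. The full remedy therefore applies only to patients not yet randomized, or to reuse of this design. For existing data the point is a limitation to report, with a partial remedy.

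**What to change.** **For any patient not yet randomized, or if the design is reused.** In the evaluation schedule, mark the pain score and current pain-medication use at History/Pre-Op. Use the same visual analog scale as the calls, completed after consent and before randomization. In the Analytical Plan, pre-specify that post-operative pain comparisons are adjusted for baseline pain and medication comparisons for baseline use.

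**For patients already randomized, given the closure.** Adjust the pain and medication comparisons for the pre-operative IKDC subjective score, state this before the data are analysed by group, and claim no change from baseline on the pain scale.

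**Cost.** About a minute of patient time at a visit where three forms are already completed, a schedule amendment, and one covariate per analysis. The fallback needs no new data collection, but it gives only partial adjustment for pain and probably little for analgesic use.
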